### **4. STUDY OBJECTIVES**

#### **4.1 Primary Objective**

- To test whether each oral dose of lasmiditan (100 and 200 mg) is non-inferior to placebo with regard to increasing blood pressure in healthy elderly subjects ( $\geq 65$  years of age).

#### **4.2 Secondary Objectives**

- To determine the PK of lasmiditan in healthy elderly subjects ( $\geq 65$  years of age) following single 100 and 200 mg oral doses of lasmiditan.
- To assess the safety and tolerability of 100 and 200 mg oral doses of lasmiditan in healthy elderly subjects.

### **5. STUDY DESIGN**

This is a randomized, subject- and investigator-blind, crossover study with 3 treatment periods in healthy elderly subjects.

The treatments are as follows:

- Treatment A: Lasmiditan 200 mg
- Treatment B: Lasmiditan 100 mg
- Treatment C: Placebo

Each subject will be randomized to 1 of 6 treatment sequences in a Williams design, as outlined in Table 1.

**Table 1. Sequences in Study LAIG**

Sequence	Period 1	Period 2	Period 3
1	Lasmiditan 200 mg	Lasmiditan 100 mg	Placebo
2	Lasmiditan 100 mg	Placebo	Lasmiditan 200 mg
3	Placebo	Lasmiditan 200 mg	Lasmiditan 100 mg
4	Placebo	Lasmiditan 100 mg	Lasmiditan 200 mg
5	Lasmiditan 200 mg	Placebo	Lasmiditan 100 mg
6	Lasmiditan 100 mg	Lasmiditan 200 mg	Placebo

#### Screening Period

All subjects will participate in a screening visit up to 28 days prior to study drug dosing.

#### Dosing Period

Subjects will participate in 1 inpatient period involving 3 treatment periods. Subjects will be admitted on Day -1 and will be randomized to 1 of 6 treatment sequences to receive lasmiditan or placebo on Days 1, 3, and 5. There will be a washout period of approximately 48 hours between each dosing day. Subjects may be discharged on Day 7 based on investigators' discretion.

All subjects will be discharged from the study approximately 2 days after their final dose of lasmiditan or placebo.

## **6. TREATMENTS**

The following is a list of the study treatment abbreviations that will be used in the TFLs.

Study Treatment Name	Treatment order in TFL
100 mg Lasmiditan	1
200 mg Lasmiditan	2
Placebo	3

## **7. SAMPLE SIZE JUSTIFICATION**

Up to 36 subjects may be enrolled to ensure 30 subjects complete the study. Assuming a 1-sided significance level of 0.05, a standard deviation (SD) for the within-subject change in systolic blood pressure (SBP) of 6.0 mmHg (a slightly larger estimate than that seen in Study LAHA), and a non-inferiority margin of 10 mmHg, this sample size will result in at least 90% power to

---

detect a true increase of 5 mmHg in the mean within-subject change for lasmiditan 200 mg compared with placebo.

## **8. DEFINITION OF ANALYSIS POPULATIONS**

The “Safety” population will consist of all enrolled subjects, whether or not they completed all protocol requirements.

The “Pharmacokinetic” population will consist of all subjects who received at least one dose of study drug and have evaluable PK data. Subjects may be excluded from the PK summary statistics and statistical analysis if a subject has an adverse event (AE) of vomiting that occurs at or before 2 times median time of maximum observed drug concentration ( $t_{max}$ ).

Cardiovascular analyses will be conducted on data from subjects who complete at least 1 dosing period.

PK/pharmacodynamics (PD) analyses will be conducted on data from subjects who have evaluable data in both PK and cardiovascular datasets.

All protocol deviations that occur during the study will be considered for their severity/impact and will be taken into consideration when subjects are assigned to analysis populations.

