## 2. Schedule of Activities

## Study Schedule Protocol H8H-MC-LAIG

	Screening	Inpatient Period							Discharge from Clinic or Early Term Procedures	Follow up	Comments
Procedure	-28 to -2 days prior to Day 1	Day -1	Day 1	Day 2	Day 3	Day 4	Day 5	Day 6	Day 7	Day 10 ± 2 days	
Informed Consent	X										
C-SSRS and Self Harm Supplement Form	X	X							X	X	For the C-SSRS, use Baseline Version at screening and Since Last Visit Version at all other visits.
Subject Admission to CRU		X									
Subject Discharge from CRU									X		
Randomization			X								Randomization to occur prior to dosing.
Investigational Product Administration			X		X		X				
Medical History	X	X									After screening, medical history should include interim medical history.
AEs and Medication review	X	X	X	X	X	X	X	X	X	X	
Height	X										
Weight	X										
Temperature	X										
Vital Signs (supine)	X	X	Pre-dose and 4 h	24 h	Pre-dose and 4 h	24 h	Pre-dose and 4 h	24 h	X a	X	Vital signs will be single measures. The pre-dose measure is taken

										before the ABPM recordings are started. Time points may be added if warranted and agreed upon between Lilly and the investigator.
--	--	--	--	--	--	--	--	--	--	--

	Screening	Dosing Period							Discharge from Clinic or Early Term Procedures	Follow up	Comments
Procedure	-28 to -2 days prior to Day 1	Day -1	Day 1	Day 2	Day 3	Day 4	Day 5	Day 6	Day 7	Day $10 \pm 2$ days	
Orthostatic Vital Signs	X										
Ambulatory Blood Pressure Monitoring			X		X		X				The ABPM device will be worn for approximately 2 hours before dosing and will continue to be worn until the 24-hour postdose assessment is complete. See Section 9.4.2.1 for details.
ABPM Training		X									Subjects should be trained on the ABPM device on the evening of Day -1. Data from this acclimation period will not be stored or analyzed.
Clinical Laboratory Tests	X	X							X		See Appendix 2 , Clinical Laboratory Tests, for details.
Ethanol Test		X									See Appendix 2 , Clinical Laboratory Tests, for details.

Urine Drug Screen	X	X									See Appendix 2 , Clinical Laboratory Tests, for details.
Physical Examination	X	X		X		X		X	X	X	Full physical examination at screening. Symptom-driven physical examination for all other time points.
12-lead ECG	X		Pre-dose and 4 h	24 h	Pre-dose and 4 h	24 h	Pre-dose and 4 h	24 h			Single ECG readings will be taken. The pre-dose measure is taken before the ABPM recordings are started.

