## 7.3. Blinding

This study will be subject- and investigator-blind. The investigator, site staff (except unblinded pharmacy staff), and subjects will be blinded to study treatment.

Emergency codes will be available to the investigator. A code, which reveals the treatment for a specific study subject, may be opened during the study only if the subject's well-being requires knowledge of the subject's treatment assignment.

If a subject's study treatment assignment is unblinded, the subject must be discontinued from the study, unless the investigator obtains specific approval from a Lilly clinical pharmacologist (CP) or CRP for the study participant to continue in the study. During the study, emergency unblinding should occur only by accessing the study subject's emergency code.

In case of an emergency, the investigator has the sole responsibility for determining if unblinding of a subject's treatment assignment is warranted for medical management of the event. The subject's safety must always be the first consideration in making such a determination. If the investigator decides that unblinding is warranted, it is the responsibility of the investigator to promptly document the decision and rationale and notify Lilly as soon as possible.

Upon completion of the study, all codes must be returned to Lilly or its designee.

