### 8.2. Discontinuation from the Study

Subjects will be discontinued under the following circumstances:

- Enrollment in any other clinical study involving an investigational product or enrollment in any other type of medical research judged not to be scientifically or medically compatible with this study
- Participation in the study needs to be stopped for medical, safety, regulatory, or other reasons consistent with applicable laws, regulations, and good clinical practice (GCP)
- Investigator Decision
  - the investigator decides that the subject should be discontinued from the study

- Subject Decision
  - the subject, or legal representative, requests to be withdrawn from the study.

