#### **9.4.2.1. Ambulatory Blood Pressure Monitoring**

For each subject, ABPM will be performed according to the Schedule of Activities (Section 2).

Site investigative personnel should be trained on the correct positioning of the ABPM monitor, use of correct cuff size, and monitor calibration prior to the start of the study. Subjects should be trained on the ABPM device on the evening of Day -1 to maximize the collection of valid measurements, and to alleviate any concerns about inconvenience due to the continuous 24-hour monitoring.

The ABPM device should be attached to the subject's nondominant arm and will record ambulatory BP and PR every 20 minutes during awake hours (e.g. 0700 hours to 2200 hours) and every 30 minutes throughout the night (2200 hours to 0700 hours). On Days 1, 3, and 5 when dosing occurs, the BP and PR recording will be initiated approximately 2 hours prior to the planned dosing time and will continue for approximately 26 hours. Subjects will be encouraged to keep the same routine without strenuous activity during the ABPM recording days.

The ABPM device should be removed from each subject prior to their discharge from the CRU.

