## **9. STATISTICAL METHODOLOGY**

### **9.1 General**

Data listings will be provided for all data that are databased. Summary statistics and statistical analysis will only be presented for data where detailed in this SAP. For continuous data, summary statistics will include the arithmetic mean, arithmetic SD, median, min, max and N; for log-normal data (e.g. the PK parameters: are under the concentration versus time curve [AUCs] and maximum observed drug concentration [ $C_{max}$ ]) the geometric mean and geometric coefficient of variation (CV%) will also be presented. For categorical data, frequency count and percentages will be presented. Data listings will be provided for all subjects up to the point of withdrawal, with any subjects excluded from the relevant population highlighted. Summary statistics and statistical analyses will generally only be performed for subjects included in the relevant analysis population. For the calculation of summary statistics and statistical analysis, unrounded data will be used.

Mean change from baseline is the mean of all individual subjects’ change from baseline values. Each individual change from baseline will be calculated by subtracting the individual subject’s baseline value from the value at the timepoint. The individual subject’s change from baseline values will be used to calculate the mean change from baseline using a SAS procedure such as Proc Univariate.

Data analysis will be performed using SAS® Version 9.4 or greater.

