## 9.4 Cardiovascular Assessment

### 9.4.1 Cardiovascular Analysis

The primary parameter for the cardiovascular analyses will be peak hourly mean values of SBP, and will be determined using ambulatory blood pressure monitoring (ABPM). For each subject, the mean SBP value will be calculated for each hour within the dosing period. The highest mean value across the 24 calculated means will be considered the peak hourly mean value. Baseline value will be defined as the mean value during the 2 hours pre-dose for each period.

Additional analysis will be performed if warranted upon review of the data.

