The following gatekeeping procedure will be used to adjust for multiplicity when conducting the hypothesis tests. The null hypothesis that the difference in mean baseline change between lasmiditan 100 mg and placebo is at least 10 mmHg will first be tested against the alternative hypothesis that this difference is less than 10 mmHg. If the p-value for this test is less than 0.05, then there is significant evidence that lasmiditan 100 mg is non-inferior to placebo and these hypotheses will be re-tested using lasmiditan 200 mg. Otherwise, if the p-value is at least 0.05, then there is no significant evidence that lasmiditan 100 mg is non-inferior to placebo, in which case the null and alternative hypotheses will not be re-tested using lasmiditan 200 mg.

A sensitivity analysis will be performed on subjects who complete all 3 dosing periods. In addition, sensitivity analyses will be conducted where baseline value is the mean SBP value during the 1 hour pre-dose for each period. These analyses will be performed separately on subjects who complete at least 1 dosing period and on subjects who complete all 3 dosing periods. The same mixed-effects model as that was used in the primary analysis will be implemented.

A repeated measures analysis will also be conducted in which changes from baseline in hourly mean values of SBP will be analyzed to test whether each dose of lasmiditan (100 mg, 200 mg) is non-inferior to placebo at each time point (hour), assuming a non-inferiority margin of 10 mmHg. A repeated measures linear mixed-effects model with baseline as a covariate, fixed effects for time point, treatment, period, treatment sequence, and the treatment by time point interaction, and a random effect for subject will be used to conduct the tests at a 1-sided significance level of 0.05. An unstructured covariance structure will be applied. If the model fails to converge, alternative structures shall be examined using Akaike's criteria. At each time point, LS means and treatment differences (lasmiditan 200 mg – placebo, lasmiditan 100 mg - placebo) will be calculated and presented with their corresponding 95% CIs, from which non-inferiority of lasmiditan (100 mg, 200 mg) to placebo will be determined if the upper confidence limit is less than 10 mmHg.

An example of the SAS code that will be used is as follows:

```
proc mixed data=xxx;
  class trtmnt time period seq subject;
  model cardiochg = base time trtmnt period seq trtmnt*time / alpha=0.05 cl ddfm=kr;

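### Does limiting the ABPM systolic analyses to subjects who complete a dosing period bias the test toward noninferiority?

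*SAP*

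**What the plan says.** SAP section 8, like Protocol 10.3, states: "Cardiovascular analyses will be conducted on data from subjects who complete at least 1 dosing period". Neither document defines completion of a dosing period. The nearest guide is the endpoint in SAP 9.4.1: "The highest mean value across the 24 calculated means will be considered the peak hourly mean value". The Schedule of Activities points the same way, since the monitor "will continue to be worn until the 24-hour postdose assessment is complete".

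The sensitivity analyses in SAP 9.4.2 use the three-period completers, and then repeat both sets with a 1-hour baseline: "These analyses will be performed separately on subjects who complete at least 1 dosing period and on subjects who complete all 3 dosing periods". No planned ABPM systolic analysis therefore uses all dosed subjects. The safety set does include all enrolled subjects, but the ABPM items named for safety in Protocol 10.3.1.2 are diastolic pressure and pulse rate.

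On early exit, Protocol 8.2 includes the case where "the investigator decides that the subject should be discontinued from the study". Protocol 7.3 says that if a subject's "study treatment assignment is unblinded, the subject must be discontinued from the study", unless the sponsor's physician approves otherwise. Protocol 9.4.2.1 says "The ABPM device should be removed from each subject prior to their discharge from the CRU". On reporting, SAP 9.1 says "Data listings will be provided for all subjects up to the point of withdrawal, with any subjects excluded from the relevant population highlighted".

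**The concern.** Membership of the cardiovascular set depends on something that happens after dosing and that the drug could influence. The study exists because an earlier study (LAHA) showed a mean maximum systolic rise of 14.5 mmHg in elderly subjects on 200 mg. If the subjects with the largest rises left before their first 24-hour recording ended, the lasmiditan mean would be too low and the test too easy to pass. A loss in a 100 mg-first subject would affect the gatekeeping comparison, and a loss in a 200 mg-first subject the second comparison.

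The sensitivity analyses would not reveal this, because each uses the same rule or a stricter one. Supine vital signs are a weak substitute. They are scheduled at 4 and 24 hours after the dose, whereas the earlier rise was maximal at about 1.5 hours and was returning toward baseline by 3 hours.

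**Working it through.** **The plan's own figure.** Inputs from SAP section 7: 30 completers, SD 6.0 mmHg, margin 10, true difference 5, one-sided alpha 0.05. Reading 6.0 as the within-subject SD, the standard error of a treatment difference is 6.0 × √(2/30) = 1.549. Power = Φ((10 − 5)/1.549 − 1.645) = Φ(1.58) = 94.3%, consistent with the stated minimum of 90%. With 27 completers it is still 92.2%, so a few losses do not threaten power.

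**How a subject would be lost.** Four things must all happen: the subject is in Period 1; exit comes before 24 hours; exit is caused by blood pressure; and the monitor stops at exit. The documents make the last one doubtful.

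- The dose is single and already taken, so stopping treatment does not shorten the current period.
- The Schedule of Activities keeps the monitor on through the 24-hour assessment.
- Protocol 9.4.2.1 ties removal to discharge from the unit, not to discontinuation.
- Protocol 3.3 has subjects monitored in the unit for at least 48 hours after each dose.
- The early-termination column has no ABPM entry, but it is shared with Day 7 discharge, and ABPM is scheduled only on Days 1, 3 and 5.
- Protocol 3.2 reports 18 elderly subjects on 200 mg in the earlier study and no discontinuations due to adverse events.

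**Size if one subject is lost.** Take the planned mixed model without the baseline covariate: treatment, period and sequence fixed, subject random, within-subject SD 6. Add to 30 completers (5 per sequence) one 200 mg-first subject with a Period 1 value only. The shift in the 200 mg − placebo estimate is the subject's weight times the excess over the value predicted from the others. The between-subject SD and the 20 mmHg excess are assumptions; the documents give neither.

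| Between-subject SD | Weight | Shift at 20 mmHg | SE |
|---|---|---|---|
| 3 | 0.0236 | 0.47 | 1.540 |
| 6 | 0.0144 | 0.29 | 1.544 |
| 10 | 0.0075 | 0.15 | 1.546 |

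As 1 of 36 enrolled, the shifts are 0.42, 0.26 and 0.13, with SE about 1.43. Two lost subjects added to 30 completers give 0.92, 0.57 and 0.30. A lost placebo-first subject shifts both contrasts the other way. The largest single shift is 0.47/1.54 = 0.31 of a standard error, and it needs an extreme subject: with between-subject SD 3 the total SD is √(9 + 36) = 6.7, so 20 mmHg is about 3 SDs.

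**Error rate at the margin.** Simulation with the true 200 mg difference at exactly 10 mmHg (12,000 trials per setting, Monte Carlo error about 0.2 points):

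| Rule for 200 mg-first subjects | Bias (mmHg) | False pass |
|---|---|---|
| Top 3% of Period 1 responses lost | −0.05 to −0.13 | 5.5–5.9% |
| Top 10% lost | −0.18 to −0.37 | 6.2–8.1% |
| Value kept, as if fully observed | +0.01 to −0.06 | 4.9–5.5% |

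Two of the six sequences start with 200 mg, so 10 to 12 subjects do. The top 10% is then about one subject per trial, and the top 3% about a third of one. At the planned true difference of 5 mmHg, with 30 subjects and the top 10% lost, the pass rate is 95.0–96.0% against 93.3–93.6% when kept.

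**Whether the subject could be put back.** For independent hourly means, the expected maximum is 1.95 SD over 24 hours and 0.85 SD over 3, a gap of 1.10 SD. With an assumed hourly SD of 6 to 10 mmHg that is 6.6 to 11 mmHg; allowing for autocorrelation it is about 7 to 12. A peak from a 3-hour recording would thus be understated by about that much with no drug effect. Requiring a complete period protects the endpoint against this.

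**The case for a change.** The best case for a change runs as follows. The error, if it occurs, favours declaring the drug safe. A noninferiority test has to protect at the margin, where false passes could reach 6.2–8.1%. Discontinued subjects may be replaced, so the target of 30 completers could be met while an early exit goes unmodelled. Completion is undefined, and with dosing every 48 hours a longer reading is possible. There is no rule for a partial recording in Period 2 or 3. A supportive analysis of all dosed subjects through the planned hourly model would need no new data.

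The textual points stand. The error rates assume that every subject in the top tenth leaves with the recording cut short, which the monitoring arrangements make unlikely. A supportive analysis would leave the primary test and its error rate where they are. The 4.9–5.5% comparator is not attainable in practice, because it treats an early leaver's peak as fully observed.

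A cruder measure spreads the excess over all dosed subjects: 20/36 = 0.56 mmHg, giving Φ(0.56/1.549 − 1.645) = 10.0%. That applies only if the whole excess is a lasting treatment effect peculiar to that subject. Restoring one Period 1 value, with no placebo value from the same subject, would recover only 0.13 to 0.42 mmHg of it.

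The undefined terms have a natural reading. A peak over 24 hourly means implies that a period is complete when its 24-hour recording is. By the same definition, a recording that stops early has no peak for that period, and the mixed model uses the subject's other periods.

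**Conclusion.** The rule is a post-dose condition and no planned ABPM systolic analysis avoids it, but following the plan as written would still give a sound conclusion. A subject stopped for a pressure rise would ordinarily complete the 24-hour recording and be analysed. If one 200 mg-first subject were nevertheless lost, the estimate would fall by about 0.15 to 0.47 mmHg (30 completers, within-subject SD 6, between-subject SD 3 to 10, assumed 20 mmHg excess), less than a third of a standard error. With no such loss the effect is zero, and at the planned 5 mmHg difference the conclusion would rarely change.

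An early exit would not be hidden either. Readings up to withdrawal are listed with the exclusion highlighted (SAP 9.1), disposition is listed (SAP 9.2), adverse events are summarised by treatment for all enrolled subjects (SAP 8 and 9.5.1), and SAP 9.4.1 allows further analysis if the data warrant it. This is missing detail that analysts would fill sensibly. The judgement would weaken only if several subjects had recordings cut short in Period 1 and the true difference lay close to 10 mmHg.

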## **9. STATISTICAL METHODOLOGY**

### **9.1 General**

Data listings will be provided for all data that are databased. Summary statistics and statistical analysis will only be presented for data where detailed in this SAP. For continuous data, summary statistics will include the arithmetic mean, arithmetic SD, median, min, max and N; for log-normal data (e.g. the PK parameters: are under the concentration versus time curve [AUCs] and maximum observed drug concentration [ $C_{max}$ ]) the geometric mean and geometric coefficient of variation (CV%) will also be presented. For categorical data, frequency count and percentages will be presented. Data listings will be provided for all subjects up to the point of withdrawal, with any subjects excluded from the relevant population highlighted. Summary statistics and statistical analyses will generally only be performed for subjects included in the relevant analysis population. For the calculation of summary statistics and statistical analysis, unrounded data will be used.

Mean change from baseline is the mean of all individual subjects’ change from baseline values. Each individual change from baseline will be calculated by subtracting the individual subject’s baseline value from the value at the timepoint. The individual subject’s change from baseline values will be used to calculate the mean change from baseline using a SAS procedure such as Proc Univariate.

Data analysis will be performed using SAS® Version 9.4 or greater.

